Randomized Controlled Trial of Preoperative Steroids in
Autoimmune Thyroid Disease

NCT04542278

DOCUMENT DATE: 10/22/2020

Randomized Controlled Trial of Preoperative Steroids in Autoimmune Thyroid Disease

- [name], University of Wisconsin, Madison
- Protocol Version Date: April 2020
- Coordinating Center Identification: N/A
- Co-Investigators: [name], [name], [name]
- Study Coordinator: N/A
- Funding Sponsor: UW-Madison Department of Surgery, American Association of Endocrine Surgeons

Abbreviations:

AE = adverse event

ATA = American Thyroid Association

Ca = Calcium

FT4 = thyroxine

HIPAA = Health Insurance Portability and Accountability Act

Ig = Immunoglobulin

PHI = protected health information

PTH = parathyroid hormone

QoL = quality of life

RAI = radioactive iodine

RLN = recurrent laryngeal nerve

SAE = serious adverse event

SF-12 = 12 question Short Form Health Survey

TgAb – Thyroglobulin Antibody

ThyPRO = thyroid-specific quality of life patient-reported outcome measure for benign thyroid disorders

TNF = tumor necrosis factor

TPO – Thyroid peroxidase antibody

TRAb – Thyrotropin Receptor antibody

TSI – Thyroid Stimulating Ig antibody

TSH = thyroid stimulating hormone

Project Summary:

Graves' disease and Hashimoto's thyroiditis are autoimmune conditions affecting the thyroid gland. Surgery to remove the thyroid gland in these patients may be complicated by the inflammatory nature of these diseases. Prednisone is a steroid medication used to decrease inflammation of the thyroid gland in other disease states such as sub-acute thyroiditis, but has not been used systematically to reduce inflammation in patients about to undergo surgery. This is a small pilot project that proposes to randomize a small sample of patients about to undergo surgery for their autoimmune, inflammatory thyroid disease, and determine if a short course of prednisone alters the inflammation of the gland and makes surgery less difficult. This could potentially lead to better outcomes for these patients, as well as increased time to recovery and improved quality of life. This project proposes to administer short quality of life surveys at three time points, as well as draw additional labs to measure antibody levels at times when patients will already be getting labs drawn for clinical purposes. The purpose of this study is to generate preliminary data from which a larger, blinded, placebo-controlled trial could be designed.

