We hypothesize that administering a course of steroids to patients with Graves' or Hashimoto's thyroiditis prior to thyroidectomy will result in a less difficult thyroid operation (measured by a previously validated scale) and a lower rate of surgical complications. Furthermore, we hypothesize administering steroids will results in faster improvement in antibody levels, antibody mediated cytokine levels, and health care quality of life as measured by surveys.

Over the past 5 years, our group has performed nearly 350 thyroidectomies for Graves' or Hashimoto's thyroiditis, giving us nearly 70 potential subjects per year. We have extensive qualitative methods experience and ability to collect QoL data from our recent clinical trial on prophylactic central neck dissection for patients with differentiated thyroid cancer. We developed and validated an instrument to quantify the difficulty of thyroid surgery. This project will be a small pilot that is a non-blinded, randomized trial of patients of glucocorticoids in patients about to undergo surgery for autoimmune thyroid disease. The primary aim of this pilot is really feasibility for the definitive trial: determining willingness of participants and clinicians to

enroll, rates of follow up and response to questionnaires, and time needed for recruitment, collection of data and analysis. The specific aims are for the larger, definitive trial, but will be assessed for this small pilot.

These specific aims are:

- **Determine the benefits and safety of preoperatively administered prednisone for patients with autoimmune thyroid disease undergoing thyroidectomy on:**
 - **Difficulty of surgery^{6,10} and rates of surgical complications**
 - **Serum autoantibody levels**
- **Longitudinally assess the impact of surgical treatment on QoL in patients with autoimmune thyroid disease**

Outcomes:

- Primary
 - Thyroid difficulty Scale score
 - Autoantibody levels
 - QoL scores (12 question Short Form Health Survey [SF-12], thyroid-specific quality of life patient-reported outcome measure for benign thyroid disorders [ThyPRO])
- Secondary
 - Ultrasound doppler quantification of blood flow
 - Surgical complications (parathyroid hormone [PTH] level, recurrent laryngeal nerve [RLN] injury)

Research Design and Methods:

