- Exclusion Criteria: Pediatric patients < 18. Prior treatment with radioactive iodine (RAI). Known diagnosis of thyroid cancer. Diabetic patients. Patients on any immunosuppressive regimen (such as organ transplant patients or patients treated for other autoimmune condition). Pregnant patients. Patients being treated for active infection. Any patient for whom the surgeon feels steroids would provide a clear benefit (ie. Extremely high auto-antibody levels with a very large, inflamed thyroid gland) will be treated according to the clinical judgement of the surgeon. If a surgeon feels steroids are indicated and prescribes them, the patient will not be eligible for the trial.
- Subject identification and recruitment. We will identify patients from our own clinic who have been referred to us for consideration of thyroidectomy as treatment for their autoimmune thyroid disease. Each surgeon spends time prior to each clinic looking through their patient list, and will flag anyone with an autoimmune thyroid disease coming to discuss thyroidectomy as a potential study participant. After the normal clinical consult, those patients who choose to undergo thyroidectomy and otherwise meet criteria will be given the opportunity to participate in the trial. This will all occur in the same physical setting of our UW endocrine surgery clinic.
- Because this is a small pilot study done with limited resources and designed for feasibility and generating preliminary data, patients and surgeons will not be blinded to treatment. The operating surgeon is typically the provider who does the preoperative assessment and provides medications and instructions directly to the patient, and we lack the resources to coordinate a study-specific preoperative visit.
 - Because participants are not blinded, knowledge of their group assignment may affect their behavior. Subject non-blinding should not affect our primary outcomes of thyroid difficulty, serum antibody, or cytokine levels. It may alter their responses on the QoL surveys, however, as steroids can cause a euphoric effect while a person is taking them. QoL surveys are to be administered before the study begins, and then not again until 6 weeks and 6 months after surgery when subjects are no longer taking the steroids, so the effect will be minimal. For secondary outcomes, subject non-blinding should not affect ultrasound measurements or surgical outcomes.

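### The assurance that open-label bias in the QoL scores will be minimal covers steroid euphoria only, not patients' continuing knowledge of their arm

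*Combined protocol and SAP*

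**What the plan says.** The bullet on non-blinding under Research Design and Methods states that "patients and surgeons will not be blinded to treatment", and the Study Drug section specifies no placebo. The non-blinding text opens with the general concern: "Because participants are not blinded, knowledge of their group assignment may affect their behavior". It names thyroid difficulty, serum antibodies and cytokines as primary outcomes that patient non-blinding should not affect, and then takes QoL as the exception: "It may alter their responses on the QoL surveys, however, as steroids can cause a euphoric effect while a person is taking them". The concern is closed by timing. The surveys are given at the start and then at 6 weeks and 6 months after surgery, "when subjects are no longer taking the steroids, so the effect will be minimal".

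The next paragraph treats surgeons differently. It accepts that their difficulty ratings may be altered by knowing the treatment, and judges this an acceptable price for easier enrolment.

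SF-12 and ThyPRO stand under Primary in the Outcomes list. The hypothesis in Specific Aims/Study Objectives ties QoL to the drug: "we hypothesize administering steroids will results in faster improvement in antibody levels, antibody mediated cytokine levels, and health care quality of life". Statistical Considerations analyses all primary aims for the effect of treatment group, by a mixed-model two-way analysis of variance with t-tests where suitable, and then uses that analysis for the sample size of the future study. The Project Summary gives the pilot's purpose as to "generate preliminary data from which a larger, blinded, placebo-controlled trial could be designed".

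**The concern.** The protocol raises one problem and answers another. The problem raised is that patients know their assignment. The answer given is that a pharmacological effect will have worn off. Euphoria from prednisone would arise under a blind as well, so its disappearance says nothing about bias from being unblinded. Patients who have heard the study rationale, and who either did or did not receive the added treatment, know this just as well at 6 months as at the start.

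Two things are at stake. First, a difference between arms in SF-12 or ThyPRO would combine any effect of prednisone with any effect of knowing the arm, and the design offers no means of dividing the two. Second, the pilot feeds the planning of a blinded, placebo-controlled trial, in which the second component should largely vanish. If the pilot's QoL difference were taken over as the effect to expect, that trial could be too small.

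**Working it through.** **Reasoning, step by step**

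- Bias source named in the text: knowledge of group assignment. It lasts from randomization to the end of follow-up, because there is neither blinding nor placebo.
- Mechanism discussed for QoL: euphoria while on the drug. It is confined to the 7 preoperative days of prednisone.
- Safeguard offered: surveys at 6 weeks and 6 months. This removes the second item and leaves the first untouched.
- Other safeguards for QoL: none described.

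**Is a between-arm QoL comparison planned?** Yes. QoL is listed as primary, and all primary aims are analysed for treatment group.

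**Is there a planned figure to reproduce?** No. The 30 patients rest on a recruitment estimate. The plan states no significance level, power, effect size or SD for QoL.

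**Illustration of what an unaddressed shift could do.** Inputs from the protocol: 15 patients per arm. Assumed inputs: a two-sided 5% two-sample t-test, complete data, no true drug effect, and a reporting shift of b SD between arms. The documents give no value for b, so a range is shown.

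- Degrees of freedom: 15 + 15 − 2 = 28. Critical value: t(0.975, 28) = 2.048.
- Noncentrality: b × √(15/2) = 2.739b.
- Rejection probability: P(|T| > 2.048), with T noncentral t on 28 df.

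| Assumed shift b | Noncentrality | Chance of a significant result |
|---|---|---|
| 0 | 0 | 5.0% |
| 0.2 SD | 0.548 | 8.3% |
| 0.3 SD | 0.822 | 12.5% |
| 0.5 SD | 1.369 | 26.2% |

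These rates apply to each QoL score at each visit. The 95% confidence interval for a difference has half-width 2.048 × √(2/15) = 0.75 SD, wider than every shift in the table.

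**Illustration for the next trial.** Further assumptions: 80% power, two-sided 5%, normal approximation, and the pilot's observed difference adopted as the planning effect d. Then n per arm = 2 × (1.960 + 0.842)² / d² = 15.70 / d².

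- True effect 0.3 SD plus shift 0.2 SD, read as 0.5 SD: planned n = 15.70 / 0.25 = 62.8, so 63 per arm. Needed: 15.70 / 0.09 = 174.4, so 175 per arm. Power achieved with 63: Φ(0.3 × √(63/2) − 1.960) = Φ(−0.276) = 39%.
- True effect 0.5 SD plus shift 0.2 SD, read as 0.7 SD: planned n = 15.70 / 0.49 = 32.04, so 33 per arm. Needed: 63. Power achieved with 33: Φ(0.5 × √(33/2) − 1.960) = Φ(0.071) = 53%.

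**The case against.** The strongest reply is that this is an openly unblinded feasibility pilot. Specific Aims says that feasibility is the real primary aim and that the listed aims belong to the definitive trial. The formal QoL aim concerns the impact of surgery over time, not of prednisone. The protocol explains why blinding was out of reach, and it foresees a blinded successor. It also admits that QoL answers may be altered, and the assurance can be read as referring only to the euphoria just mentioned, for which the timing argument is sound. Both arms undergo total thyroidectomy after a short preoperative course, so any residual effect of knowing the arm at 6 weeks or 6 months could be small.

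Much of this stands, and it limits the weight of the point. It does not close the gap. The same section says that the specific aims will be assessed in the pilot, the hypothesis credits steroids with faster QoL improvement, and the treatment-group analysis leads into the next sample size. If the assurance is meant for euphoria only, then knowledge of the arm has received no answer for QoL.

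Three stronger readings should be resisted:

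- A reader might infer that the non-blinding text drops QoL from the primary outcomes, because the sentence naming primary outcomes omits it. In context that sentence lists the outcomes thought to be unaffected. QoL follows as the exception, before the text turns to secondary outcomes, which agrees with the Outcomes list.
- A reader might infer that reporting bias will occur, or that any QoL difference is not due to prednisone. The documents show neither. They show only that the two explanations cannot be told apart.
- A reader might infer that the observed QoL difference will set the size of the next trial. Statistical Considerations says that the analysis will inform that calculation. It does not say which quantity will be used, nor that QoL will drive it.

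**Conclusion.** The point holds as a gap in reasoning with a modest consequence. The assurance of a minimal effect is supported for steroid euphoria and unsupported for knowledge of the arm. A between-arm difference in SF-12 or ThyPRO at either follow-up cannot be separated from the effect of knowing the arm.

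The size of that effect cannot be had from the documents. The range of about 8% to 26% is correct arithmetic on an assumed shift of 0.2 to 0.5 SD. It is not an estimate of this trial's error rate, and its upper end depends wholly on the upper assumption. It also uses a plain t-test at an assumed 5% level, whereas the plan names a mixed model first and states no level. The planning figures carry the added assumption that the observed difference would be used as the effect. The conclusion about separability needs none of these numbers. It follows from no blinding, no placebo and self-reported outcomes.

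**What to change.** 1. In the non-blinding text under Research Design and Methods, limit the statement that the effect will be minimal to the euphoric effect. Add that knowledge of the arm can affect QoL answers at both 6 weeks and 6 months, with the same candour as the following paragraph shows about the surgeon's difficulty scale.
2. In Outcomes and in Statistical Considerations, keep QoL collection as it is, but label the between-arm QoL comparison exploratory.
3. In the sample-size step of Statistical Considerations, state that QoL variability and response rates will be taken from the pilot, and that the observed between-arm QoL difference will not be used as the effect expected in the blinded, placebo-controlled trial.

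The cost is wording only. Visits, surveys, treatment and budget do not change. The one small loss is that the pilot gives up a between-arm claim on QoL.

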 - Because surgeons are not blinded, it is possible that their responses for the thyroid difficulty scale will be altered by their knowledge of whether the subject took steroids. The logistics of having the patients leave the surgeons clinic not knowing their group assignment, then having a different researcher assign and provide the medication would be beyond the budget and capabilities of our team for this feasibility trial. We feel the benefits of ease of enrollment and ability to recruit sufficient patients outweigh the possible bias in the thyroid difficulty scale.
- There are no additional collaborating sites – this will all be performed at UW Hospitals and Clinics
- Identify information extracted from medical records – demographics, length of time of disease, lab values related to thyroiditis disease, indications for surgery,

surgical data including blood loss and length of operation, postoperative laboratory values related to thyroiditis.

- We know that glucocorticoids may decrease Immunoglobulin (Ig)G and IgA levels with moderate-to-high dose steroids given over short term. (10-20 percent at one week in rheumatoid arthritis patients)¹³, therefore we intend to collect serum for antibody levels at intervals more frequent than our standard of care.
- **Specimen/data collection, handling, storage**
 - Data will be collected electronically (REDCap) on the Institute for Clinical and Translational Research (ICTR) secure version of the software and on paper. The only data recorded on paper will be the Thyroid difficulty scale and the prednisone compliance survey and these will be stored in the PI's office in a locked file cabinet.
 - All information obtained and associated data files will be confidential and will be kept in a locked file or password protected secure departmental server through the department of surgery (U:). This server is backed up according to standard protocols. All computers used to access this server are password protected. The risk of breach of confidentiality regarding participation in the study outside of the scope of the research will be handled by carefully controlling access to study data only to personnel on the research team.

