- Day of Surgery: Surgeon will repeat the ultrasound in the operating room to compare area of blood flow. As part of the clinical workup, each surgeon always performs thyroid ultrasound using our GE Logiq clinic equipment, and this includes a single image using "doppler" mode to measure blood flow. Surgeons then do an ultrasound once the patient is positioned in the operating room to verify incision placement, and for study patients we will save one "Doppler" image for comparison purposes to the preop image. While the single image is unique to this study, performing the ultrasound is part of our routine clinical care and saving one additional image takes 10 seconds and confers no additional risk. There is no charge for this image and it will be uploaded with the clinical image to the radiology digital storage system for the surgeons to compare blood flow from before and after steroid administration. Research specific blood draw (15mL) will occur at the time of IV placement and sent for antibody levels. Patients will be asked whether they took their course of steroids as described and we will record their answers. If they report not taking it as directed, their narrative reasons for not doing so will be recorded. Total thyroidectomy will be performed using standard techniques in all patients potentially eligible for randomization. An open technique will be used to remove the entire thyroid including pyramidal lobe and all visible thyroid tissue. Care will be taken to visualize and preserve both recurrent laryngeal nerves and to preserve all parathyroids *in situ*. All removed specimens will be carefully examined for any parathyroid tissue and any devascularized or resected normal parathyroid glands will be confirmed by frozen section and autotransplanted into the sternocleidomastoid muscle, as per our standard of care. The surgeon will then fill out the "Thyroid Difficulty Scale" at the conclusion of the operation, either by the surgeon entering it directly into the secure RedCap project or recording their answers on paper that is coded and entered later. If on paper and coded, surgeons will store the paper separately from any PHI related to that subject and will destroy the paper as soon as it is entered into the database.

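### The Doppler blood-flow images are to be compared by unblinded surgeons with no masked reading described, and the protocol's discussion of surgeon bias leaves this outcome out

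*Combined protocol and SAP*

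**What the plan says.** Outcomes lists "Ultrasound doppler quantification of blood flow" as a secondary outcome. Under Research Design and Methods the protocol states that "patients and surgeons will not be blinded to treatment", and gives the practical reason: "The operating surgeon is typically the provider who does the preoperative assessment and provides medications and instructions directly to the patient".

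The Day of Surgery item under Study Procedures reads: "Surgeon will repeat the ultrasound in the operating room to compare area of blood flow". One Doppler image is saved and "uploaded with the clinical image to the radiology digital storage system for the surgeons to compare blood flow from before and after steroid administration". The first image of the pair comes from the routine clinic ultrasound, which the schedule table places 2-4 weeks before surgery.

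The protocol reviews the consequences of non-blinding in two places, both under Research Design and Methods:

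- On subjects: "For secondary outcomes, subject non-blinding should not affect ultrasound measurements or surgical outcomes".
- On surgeons: "it is possible that their responses for the thyroid difficulty scale will be altered by their knowledge of whether the subject took steroids". It then accepts that bias, because having someone else assign and hand out the drug would exceed the team's budget and capabilities.

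Neither place considers surgeon knowledge of the arm in relation to the ultrasound outcome. No masked, coded, independent or duplicate reading of the images is described anywhere. Nor does the protocol say how the flow area is to be measured.

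**The concern.** The people named as comparing the images belong to the group that knows the allocation. The comparison is described as before and after steroids, although 15 of the 30 patients receive none. If the flow area involves any judgement, such as which region to outline or which pixels to count as flow, an expectation about steroids can enter the measurement in one arm and not the other.

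The protocol's reason for forgoing blinding concerns assigning and dispensing drug around the clinic visit. It does not extend to images that sit in a storage system and can be measured later. The difficulty score has to come from the surgeon who operated; the image measurement does not. At stake is whether a between-arm Doppler difference in the pilot can be read as an effect on the gland or only as an effect of knowing the arm.

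**Working it through.** The plan gives no figure to reproduce for this outcome. Statistical Considerations states no alpha, power, standard deviation or effect size, and bases the total of 30 on expected recruitment. The check is therefore mainly a reading of the text.

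**Which bias matters.** Write a patient's measured change in flow as true change + *o* + *b*. Here *o* is any effect of knowing which image is later, and *b* is any effect of knowing the arm. The between-arm difference is then

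(true change, steroid − true change, control) + (*o* − *o*) + (*b*, steroid − *b*, control).

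The order term is common to both arms and cancels. The arm term does not. Masking the arm is thus the essential part; masking the order is a useful extra.

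**How many images.** At full enrolment, 30 patients × 2 images = 60. Patients are approached after the normal clinical consult, so the 30 clinic images appear to be taken before allocation. If they were also quantified then, those 30 readings would precede knowledge of the arm, and bias could enter only through the 30 operating-room images. That would still be enough to shift the contrast.

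**What a shift would do (illustration only).** My assumptions are 15 per arm, a two-sided t-test at 0.05, no true effect, and a net reading shift of *b* standard deviations of the analysed quantity. The test statistic is noncentral t with 28 degrees of freedom and noncentrality *b* × √(15/2) = 2.739*b*.

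| Assumed shift (SD) | Noncentrality | Chance of a false positive |
|---|---|---|
| 0 | 0 | 5.0% |
| 0.1 | 0.274 | 5.8% |
| 0.25 | 0.685 | 10.1% |
| 0.5 | 1.369 | 26.2% |
| 0.75 | 2.054 | 50.9% |

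Nothing in the documents says where in this range the trial would fall.

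**Whether a masked read is within reach.** Both images of each pair are stored. The protocol refers to several surgeons and to co-investigators. It already puts a participant number on data collection forms, although for confidentiality and not for masking. The number of surgeons and their availability are not given, so it is a reasonable inference, not a documented fact, that a non-treating colleague could do the reads.

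**The case against.** The strongest reply is that this is an open-label feasibility pilot that discloses its lack of blinding, that Doppler is only a secondary outcome, and that the stated analysis is for the primary aims, with no Doppler test specified. This stands and limits the priority. It does not close the point: the protocol works through non-blinding outcome by outcome, and accepts surgeon bias only for the difficulty scale.

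A reader might infer several stronger things that the documents do not support:

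- *That each surgeon measures their own patients' images, knowing the arm and the order.* The text says only that the surgeons compare. Which surgeon reads, when, and how the area is measured are not stated. Automated quantification would leave no reading bias.
- *That all 60 readings are compromised.* The clinic images appear to precede allocation. Sixty is a count of images, not a size of bias.
- *That agreement between Doppler and the difficulty score would be false confirmation.* Nowhere do the documents plan to use one to corroborate the other. The direction of any bias is not derivable. Blood loss and operation length are also extracted, although not listed as outcomes.
- *That Doppler results would mis-size the definitive trial.* The pilot analysis is to inform that sample size, but nothing says this outcome will be used for it.
- *That coded reading would make the outcome unbiased at no cost.* An unblinded surgeon still takes and saves the single operating-room frame. Clinic and operating-room images may look different, so order may be hard to hide. Someone has to code and export the images, and the protocol lists no study coordinator.

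**Conclusion.** The point holds in limited form. Unblinded surgeons are to compare the stored images, no masking is described, and the bias discussion omits this combination of outcome and observer. Knowledge of the arm could bias the between-arm Doppler comparison to the extent that the flow area depends on the judgement of whoever measures it. The size is unknown. It ranges from nil with fully automated quantification upwards, and the false-positive figures above rest on assumed shifts, not on the documents. I rate this a cheap improvement of moderate priority, not a flaw that undermines the pilot, whose stated primary aim is feasibility.

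**What to change.** - In the Day of Surgery item, replace the surgeons' before-and-after comparison with a masked one. Quantify the stored images (up to 60) under study code, without the arm and, where feasible, without dates and in random order. Use a surgeon or co-investigator already in the group who neither enrolled nor operated on that patient. Unmask only for analysis.
- Apply one fixed rule for acquiring and saving the single operating-room Doppler frame, because coded reading cannot correct an unblinded choice of frame or settings.
- Add Doppler to the paragraph on surgeon non-blinding, and state there the acquisition bias that remains.

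The cost is a modest amount of coding and export work, plus reading time swapped among people already in the study. No scan, visit or patient is added, and the total stays at 30. The downside is that the comparison is made after the operations instead of case by case.
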